Within 24 hours of admission to the inpatient floor, study subjects will be approached by a member of the research team, and asked for informed consent. Patients that consent to participate and meet our inclusion criteria will be ordered the appropriate study drug by the floor pharmacist, per the Yale Investigative Drug Service's randomization to either the treatment or the placebo arm. Each subject will be ordered a capsule containing either placebo (cellulose microcrystalline) or 5 mg melatonin each evening at 9 p.m. The study drug can be given as early as 7pm on the day of admission, if necessary, to allow treatment to begin within 24 hours of admission to the floor.. The capsules will be prepared and administered by the Yale-New haven Hospital Investigational Drug Service. The capsules will be administered nightly until discharge or a maximum of 2 weeks if the hospitalization is prolonged. The capsule must be swallowed whole and not opened.

Subjects will be assessed twice daily, once in the- a.m. and again in the p.m by the floor nurses for evidence of delirium using the Short CAM (Confusion Assessment Method), which is a validated clinical tool for identifying delirium, and the current standard of practice tool for the diagnosis of delirium. This evaluation should take maximally 5 to 10 minutes to complete.

While it is considered standard of care for nurses to administer the Short CAM once daily at Yale-New Haven Hospital, the twice daily Short CAM is standard of care at the University of Connecticut Hospital but not currently at the Yale-New Haven Health System with the exception of Verdi 4 West where the CAM is administered twice a day for all patients.

The primary endpoint will be the occurrence of delirium as defined by the Short CAM by the time of discharge or prior to hospital day 15, whichever occurs first. The study drug will be continued until the primary end point of delirium is reached, discharge or hospital day 15.

The maximum period of study drug administration will be 14 days. If the patient's length of stay exceeds 14 days the patient's participation in the study will end and the subject will be recorded as having completed the study without delirium. If the primary end point of delirium is reached, the subject will have completed the study, participation will be over and the study drug will no longer be administered.

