While causes of delirium will be extracted from the chart, all investigations will be done by the primary inpatient team. The diagnosis of delirium will be communicated to the inpatient team.

Patients that agree to participate in the study will not be prescribed melatonin as a sleeping aid. All care, including medications for sleep and management of delirium will be per standard of care, as decided by the attending physician of record. If the primary team believes that melatonin is medically indicated the patient will not be enrolled or be withdrawn from the study.

4. Genetic Testing N/A

A. Describe

- i. the types of future research to be conducted using the materials, specifying if immortalization of cell lines, whole exome or genome sequencing, genome wide association studies, or animal studies are planned
- ii. the plan for the collection of material or the conditions under which material will be received
- iii. the types of information about the donor/individual contributors that will be entered into a database
- iv. the methods to uphold confidentiality

B. What are the conditions or procedures for sharing of materials and/or distributing for future research projects?

C. Is widespread sharing of materials planned?

D. When and under what conditions will materials be stripped of all identifiers?

E. Can donor-subjects withdraw their materials at any time, and/or withdraw the identifiers that connect them to their materials?

- i. How will requests to withdraw materials be handled (e.g., material no longer identified: that is, anonymized) or material destroyed)?

F. Describe the provisions for protection of participant privacy

G. Describe the methods for the security of storage and sharing of materials

5. Subject Population: Provide a detailed description of the types of human subjects who will be recruited into this study.

The study will recruit subjects \geq age 65, who are admitted to the four participating general internal medicine floors at St. Raphael's hospital.

6. Subject classification: Check off all classifications of subjects that will be specifically recruited for enrollment in the research project. Will subjects who may require additional safeguards or other considerations be enrolled in the study? If so, identify the population of subjects requiring special safeguards and provide a justification for their involvement.

- | | | |
|---|--|--|

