|  Children |  Healthy |  Fetal material, placenta, or dead fetus |
|  Non-English Speaking |  Prisoners |  Economically disadvantaged persons |
|  Decisionally Impaired |  Employees |  Pregnant women and/or fetuses |
|  Yale Students |  Females of childbearing potential | |

If patients are not competent to sign the informed consent, we will contact the healthcare proxy to provide informed consent for enrollment.

NOTE: Is this research proposal designed to enroll children who are wards of the state as potential subjects? Yes No (If yes, see Instructions section VII #4 for further requirements)

7. **Inclusion/Exclusion Criteria:** What are the criteria used to determine subject inclusion or exclusion?

Inclusion Criteria

- Age \geq 65
- Inpatient admission to general internal medicine service

Exclusion Criteria

- Expected lifespan or length of stay \leq 48 hours
- Non-English speaking
- Already taking melatonin at the time of randomization (at least one dose taken in the prior week)
- Already taking ramelteon (Rozerem) at the time of randomization (at least one dose taken in the prior week)
- Presence of delirium at the time of randomization
- Unable to take oral medications
- Subject or proxy unable to provide informed consent
- Unable to give consent within 18 hours of invitation or within 24 hours of being admitted to the medical floor
- Known allergy to melatonin
- Patients taking warfarin, nifedipine and fluvoxamine
- Patients with severe liver impairment (admission diagnosis of active liver disease such as cirrhosis or acute hepatitis)
- Unable to recall at least 2 of 3 words after distraction by asking the subject to name the days of the week backwards starting with Sunday.

8. How will **eligibility** be determined, and by whom?

A member of the research team will use the hospital EMR to screen admissions to the four participating general Internal Medicine floors for eligibility, based on the above inclusion and exclusion criteria. This will be accomplished via the OnCore and YCCI EPIC Support Services. The consent process will include a brief description of the study with an

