Another possible risk involves potential breach of confidentiality with the collection of protected patient information. All patients in the study will be initially de-identified by use of medical record number and subsequently further de-identified by receiving a study number. Paper records will be kept in a locked office and computerized records will be kept in a secure hospital computer.

10. **Minimizing Risks:** Describe the manner in which the above-mentioned risks will be minimized.

Regarding the lack of ability to take melatonin for sleep; this risk is minimal, as melatonin is rarely used as a sleeping aid on the participating services. Currently only 7.2% of patients admitted to Celantano 3 and 12.3% of patients admitted to V4 West receive melatonin for

sleep. Clinicians will continue to treat insomnia with the usual non-pharmacologic and pharmacologic methods.

All patient data will be logged in a password protected YCCI / OnCore grid that will only be accessed by study personnel. All participants in the study will be HIPAA and HSPT trained.

The investigation team will review all patients, in EPIC or in person twice per day. Any possible complications will be followed closely.

11. **Data and Safety Monitoring Plan:** Include an appropriate Data and Safety Monitoring Plan (DSMP) based on the investigator's risk assessment stated below. (Note: the HIC will make the final determination of the risk to subjects.) For more information, see the Instructions, page 24.

- a. What is the investigator's assessment of the overall risk level for subjects participating in this study?

There is minimal risk anticipated for subjects participating in this study. Melatonin is considered a safe, over-the-counter, non-prescription supplement. A recent review²⁹ concluded that "Melatonin is safe for short-term use, even when given in extreme doses. Mild adverse effects, such as dizziness, headache, nausea and sleepiness have been reported in levels corresponding to placebo treatments." Section 9 lists Micromedex's side effect profile.

- b. If children are involved, what is the investigator's assessment of the overall risk level for the children participating in this study?

Not applicable

- c. Include an appropriate Data and Safety Monitoring Plan. Examples of DSMPs are available here <http://www.yale.edu/hrpp/forms-templates/biomedical.html> for

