Note: If the YNHH IDS (or comparable service at CMHC or WHVA) will not be utilized, explain in detail how the PI will oversee these aspects of drug accountability, storage, and preparation.

4. **Use of Placebo:** **Not applicable to this research project**

If use of a placebo is planned, provide a justification which addresses the following:

a. Describe the safety and efficacy of other available therapies. If there are no other available therapies, state this.

There are currently no approved therapies for the prevention of delirium.

²⁹ Andersen, L. P., Gogenur, I., Rosenberg, J., & Reiter, R. J. (2015). The Safety of Melatonin in Humans. *Clin Drug Investig.* doi: 10.1007/s40261-015-0368-5

- b. State the maximum total length of time a participant may receive placebo while on the study.

2 weeks

- c. Address the greatest potential harm that may come to a participant as a result of receiving placebo.

There is no potential harm associated with use of placebo except as noted in section 9. The placebo will be prepared by the Yale Investigational Drug Service and will consist of cellulose microcrystalline in a capsule

- d. Describe the procedures that are in place to safeguard participants receiving placebo.

Each patient will be observed in the hospital by the research team and any complications will be noted. If the patient cannot swallow without compromise then they will be removed from the trial.

6. Use of Controlled Substances:

Will this research project involve the use of controlled substances in human subjects?

Yes No *See HIC Application Instructions to view controlled substance listings.*

If yes, is the use of the controlled substance considered:

Therapeutic: The use of the controlled substance, within the context of the research, has the potential to benefit the research participant.

Non-Therapeutic: *Note, the use of a controlled substance in a non-therapeutic research study involving human subjects may require that the investigator obtain a Laboratory Research License. Examples include controlled substances used for basic imaging, observation or biochemical studies or other non-therapeutic purposes. See Instructions for further information.*

7. Continuation of Drug Therapy After Study Closure **Not applicable to this project**

Are subjects provided the opportunity to continue to receive the study drug(s) after the study has ended?

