If yes, describe the nature of this relationship.

Several members of the research team may be working as either the resident or attending physician for the study subjects at the time of data collection. The Yale Investigational Drug Service will be doing the randomization so that all will remain blinded as to the treatment arm and the placebo arm.

6. Request for waiver of HIPAA authorization: (When requesting a waiver of HIPAA Authorization for either the entire study, or for recruitment purposes only. Note: if you are collecting PHI as part of a phone or email screen, you must request a HIPAA waiver for recruitment purposes.)

Choose one:

- For entire study
- For recruitment purposes only
- For inclusion of non-English speaking subject if short form is being used

- i. Describe why it would be impracticable to obtain the subject's authorization for use/disclosure of this data; The patients' names who are admitted to Celantano 3, Celantano 4, Verdi 5 North, and Verdi 4 West and fit our inclusion criteria will be sent to the investigators via OnCore / EPIC. Before interviewing the patient we will need to review our exclusion criteria which can be done both via EPIC chart review and with discussion with the primary team. Once we are comfortable

that the patient is a candidate for inclusion we will interview the patient and further review the inclusion and exclusion criteria and begin the invitation to consider participating in the study. By reviewing the chart and perhaps interviewing the care team we will avoid needlessly bothering some patients and be more efficient in our recruitment process.

- ii. If requesting a waiver of **signed** authorization, describe why it would be impracticable to obtain the subject's signed authorization for use/disclosure of this data; In the event that a patient does not understand and/or cannot explain back to the investigator seeking informed consent, what the study entails, but does give us his/her affirmative assent, we will seek out the LAR, in person or by phone, to obtain a surrogate consent.

By signing this protocol application, the investigator assures that the protected health information for which a Waiver of Authorization has been requested will not be reused or disclosed to any person or entity other than those listed in this application, except as required by law, for authorized oversight of this research study, or as specifically approved for use in another study by an IRB.

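### Two clinical rules remove randomised subjects from the study rather than only from the capsules, and the plan gives these subjects no outcome and states no as-randomised analysis

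*Combined protocol and SAP*

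**What the plan says.** Section V.3 (Research Plan) states: "If the primary team believes that melatonin is medically indicated the patient will not be enrolled or be withdrawn from the study". The first branch acts before randomisation and raises no issue here; the second acts afterwards. Section VI.A.4, item d, adds: "If the patient cannot swallow without compromise then they will be removed from the trial". That sentence stands under safeguards for participants on placebo, but Section VII.5 has the pharmacy randomise "so that all will remain blinded as to the treatment arm and the placebo arm", so in practice it must apply to both arms.

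The primary endpoint in V.3 is Short CAM delirium by discharge or before hospital day 15. Delirium and discharge are covered by that definition, and for a stay beyond 14 days "the subject will be recorded as having completed the study without delirium". No sentence covers a subject withdrawn under either rule. Section VII.9 ties the team's twice-daily evaluation to the time a subject remains in the study.

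Section V.12 lists delirium per admission and per patient-day as primary outcomes. It plans Fisher or chi-square tests, a risk ratio, logistic regression, Kaplan-Meier curves, a logrank test and a Cox model. It states no analysis population, no as-randomised principle, no censoring rule and no handling of missing outcomes.

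**The concern.** Both exits are triggered by something that happens to the patient after randomisation, and either may go with a different risk of delirium. Section V.2 treats sleep-wake disturbance as central to delirium, so a subject for whom the team comes to want melatonin may not be typical of the arm. The documents do not link unsafe swallowing to delirium; a connection is plausible but is an assumption.

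If outcome recording ends at exit, the per-admission comparison is no longer between the groups as randomised. Censoring leavers in the survival analyses assumes that exit is unrelated to risk, and in any case does not settle the per-admission risk ratio. Whoever analyses the data would have to choose among dropping, censoring and coding as no delirium after the data exist.

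**Working it through.** **Plan's own figure.** Inputs from V.12: two-sided 5%, 80% power, 30% versus 21% (risk ratio 0.70), 1:1. The pooled-variance two-proportion formula without continuity correction gives 367 per arm, 734 in total, as stated; power at 367 per arm is 80.0%. The enrolment target in VII.1 is also 734, so there is no allowance for lost outcomes.

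**Assumptions.** The documents give no withdrawal rate. Let w be the share of an arm that exits, and let leavers have twice the delirium risk of those who stay. If the arm's full rate is p, the rate r among stayers solves (1 − w)r + w·2r = p, so r = p/(1 + w).

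**Leavers dropped** (observed rate r):

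| Exits, placebo/melatonin | Placebo | Melatonin | Risk ratio |
|---|---|---|---|
| 5%/5% | 0.30/1.05 = 28.6% | 0.21/1.05 = 20.0% | 0.700 |
| 2%/1% | 0.30/1.02 = 29.4% | 0.21/1.01 = 20.8% | 0.707 |
| 1%/2% | 0.30/1.01 = 29.7% | 0.21/1.02 = 20.6% | 0.693 |
| 5%/3% | 0.30/1.05 = 28.6% | 0.21/1.03 = 20.4% | 0.714 |
| 3%/5% | 0.30/1.03 = 29.1% | 0.21/1.05 = 20.0% | 0.687 |

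**Leavers coded as no delirium** (observed rate (1 − w)r):

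- 5%/3%: 0.95 × 28.57% = 27.1% versus 0.97 × 20.39% = 19.8%; risk ratio 0.729.
- 3%/5%: 0.97 × 29.13% = 28.3% versus 0.95 × 20.00% = 19.0%; risk ratio 0.673.
- 5%/5%: 27.1% versus 19.0%; risk ratio 0.700.

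**No true effect** (30% in both arms), leavers dropped: 5%/3% gives 28.6% versus 29.1%, risk ratio 1.02; 3%/5% gives 0.98. The false-positive rate is about 5.3% instead of 5.0%.

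**Leavers kept and analysed as randomised**, 5% exits per arm, doubled risk, all delirium detected, 367 per arm:

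- Placebo leavers then get the full melatonin benefit: placebo rate 0.95 × 28.57% + 0.05 × (2 × 28.57% × 0.7) = 29.1%, against 21.0%. Risk ratio 0.72, power 72.2%.
- Melatonin leavers also lose their benefit: melatonin rate 0.95 × 20.0% + 0.05 × (2 × 20.0%/0.7) = 21.9%, against 29.1%. Risk ratio 0.75, power 62.0%.
- For comparison, dropping the same 5% per arm leaves 349 per arm at 28.6% versus 20.0%: power 75.3%.

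With dilution in both arms and exits of 5%/3% or 3%/5%, the as-randomised risk ratio is about 0.74 either way (21.5%/29.1% and 21.9%/29.5%).

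**The case against.** The strongest reply is that few subjects will leave. Section V.7 excludes recent melatonin or ramelteon users and anyone "Unable to take oral medications". Section V.3 keeps out patients for whom melatonin is already thought indicated, bars it as a sleeping aid during participation and leaves other sleep medication to usual care. Section V.10 says that "melatonin is rarely used as a sleeping aid on the participating services" and that insomnia will be treated by the usual methods. Poor sleep is therefore ordinarily managed inside the trial, and withdrawal is a residual clause. Blinding means exits cannot follow known assignment. All of this stands, and it limits the size of the problem. It does not supply an outcome for those who do leave. Blinding also does not stop a drug effect or chance from making exits unequal, nor make exit unrelated to risk.

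Three stronger readings are tempting and not supported:

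- That the plan directs these subjects to be dropped or censored. It is silent, and coding them as no delirium is equally open.
- That the 7.2% and 12.3% melatonin use on two floors in V.10 predicts withdrawals. Those figures describe all admissions to those floors, not trial subjects.
- That retaining leavers brings the estimate back to 0.700. This holds only if leavers keep their arm's full effect. With dilution the as-randomised risk ratio is 0.72 to 0.75 in the scenarios above, and it is a different quantity, for which 0.700 is not the benchmark.

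It is also fair that the consent pages were not available for this review, so whether chart recording may continue after withdrawal cannot be confirmed.

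**Conclusion.** The omission is clear from the text: two rules end participation after randomisation, and neither an outcome nor an as-randomised analysis is stated for those affected. The bias is real in kind and probably small. Under assumed exits of 5% and 3% with doubled risk in leavers, a true risk ratio of 0.700 is reported somewhere between 0.673 and 0.729, depending on which arm loses more and how leavers are handled; equal exits leave it at 0.700. Confidence is high that the gap exists. The number of exits, their imbalance and the direction of any bias are unknown.

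A reader might infer that the trial's result would be seriously distorted, or that the point is about power. The figures support neither: the distortion is modest at low exit rates, and the proposed change can lower power. The case rests on keeping the comparison as randomised. It should be fixed before analysis. No view is taken on when capsules should stop or who should receive open-label melatonin.

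**What to change.** In Sections V.3, VI.A.4 and V.12, distinguish stopping capsules from leaving the study. Unless consent is withdrawn, and subject to the authorisation, keep recording from the chart at least the routine once-daily Short CAM until delirium, discharge or the end of the endpoint window. Analyse every randomised subject in the assigned arm, and add a sensitivity analysis for outcomes that remain unknown.

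The work is mainly wording and chart extraction. V.3 says of current practice: "While it is considered standard of care for nurses to administer the Short CAM once daily at Yale-New Haven Hospital", and Section VIII(a) already lists the daily CAM result as a data item, so no new assessment is needed.

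There are two costs. Once-daily recording may detect less than the trial's twice-daily schedule, which is not routine across the hospital system, "with the exception of Verdi 4 West where the CAM is administered twice a day for all patients". Off-drug follow-up and open-label melatonin also dilute the contrast: with 5% exits per arm and doubled risk, power is about 72% (dilution in placebo only) or 62% (both arms), against about 75% if leavers are dropped. V.12 should therefore say that 80% power assumes 367 per arm with known outcomes and no dilution.

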Do you know of any real or apparent institutional conflict of interest (e.g., Yale ownership of a sponsoring company, patents, licensure) associated with this research project?

Yes (provide a description of that interest in a separate letter addressed to the HIC.)

No

As Chair, do you have any real or apparent protocol-specific conflict of interest between yourself and the sponsor of the research project, or its competitor or any interest in any intervention and/or method tested in the project that might compromise this research project?

Yes (provide a description of that interest in a separate letter addressed to the HIC)

No

I assure the HIC that the principal investigator and all members of the research team are qualified by education, training, licensure and/or experience to assume participation in the conduct of this research trial. I also assure that the principal investigator has departmental support and sufficient resources to conduct this trial appropriately.

ATTACHED AS A SEPARATE DOCUMENT

Chair Name (PRINT) and Signature

Date

 Department

YNHH Human Subjects Protection Administrator Assurance Statement

Required when the study is conducted solely at YNHH by YNHH health care providers.

As Human Subject Protection Administrator (HSPA) for YNHH, I certify that:

- I have read a copy of the protocol and approve it being conducted at YNHH.
- I agree to notify the IRB if I am aware of any real or apparent institutional conflict of interest.
- The principal investigator of this study is qualified to serve as P.I. and has the support of the hospital for this research project.

▪ **ATTACHED AS A SEPARATE DOCUMENT**

 YNHH HSPA Name (PRINT) and Signature

 Date

SECTION V: RESEARCH PLAN

1. **Statement of Purpose:** State the scientific aim(s) of the study, or the hypotheses to be tested.

To investigate the efficacy of melatonin for the prevention of delirium in older adults admitted to a general Internal Medicine service.

2. **Background:** Describe the background information that led to the plan for this project. Provide references to support the expectation of obtaining useful scientific data.

Introduction

Delirium is a neuropsychiatric syndrome characterized by fluctuating disturbances in consciousness, commonly seen in hospitalized adults. It is independently associated with increased mortality, slowed recovery time, and increased hospital costs^{1,2,3}.

¹ Inouye SK. Delirium in older persons. *N Engl J Med* (2006) 354:1157-1165

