explanation that the subject may receive no direct benefit from participating but patient care may in general improve if the study drug successfully prevents delirium. If the patient is interested in enrolling then the patient is asked to remember 3 words (apple, penny, and table) and then is distracted by being asked to recite the days of the week backwards starting with Sunday. If the subject can remember at least 2 of the 3 words then the entire consent is reviewed in depth and the subject is asked if he understands and if he has any questions before signing. A “teach back” will be accomplished to insure that the subject or the surrogate understands all the research aspects of the study. A Short CAM will then be performed by the investigator to evaluate for delirium. If delirium is not diagnosed via the Short CAM, the consent form will be completed and the patient entered into the trial.

9. **Risks:** Describe the reasonably foreseeable risks, including risks to subject privacy, discomforts, or inconveniences associated with subjects participating in the research.

Minimal risks are anticipated with this study however participation in the study may involve risks that are currently not known. Possible risks include the swallowing of an extra pill and the lack of ability to take melatonin for impaired sleep. While Micromedex lists side effects of melatonin, such as tachyarrhythmia, red/flushed skin, hypothermia, decreased glucose tolerance, abdominal cramps/diarrhea, confusion, decreased reaction time, sedation, sleep pattern disturbance, and worsening of depression, these are considered rare and usually with little clinical effect. A recent review in the journal *Clinical Drug Investigations* (Andersen LP, Gögenur I, Rosenberg J, Reiter RJ. *Clin Drug Investig.* 2016 Mar;36(3):169-75. doi: 10.1007/s40261-015-0368-5. PMID:26692007) concluded that the short-term use of melatonin is safe, even in extreme doses and that only mild adverse effects have been reported and are probably no different than placebo²⁹, with the possible exception of sleepiness. Other potential adverse effects include dizziness, headache, and nausea as described below, in section VI.2. Melatonin should have no major drug interactions or effects on other possible drug interventions in our subjects. Mild to moderate interactions with warfarin, nifedipine and fluvoxamine are noted in Micromedex and patients treated with these medications will not be included in the study.

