The principal investigator is responsible for monitoring the data, assuring protocol compliance, and conducting the safety reviews at the specified frequency on a monthly basis. During the review process the principal investigator will evaluate whether the study should continue unchanged, require modification/amendment, or close to enrollment.

The principal investigator or the Institutional Review Board (IRB) have the authority to stop or suspend the study or require modifications.

This protocol presents minimal risks to the subjects and adverse events or other problems are not anticipated. In the unlikely event that such events occur, Reportable Adverse Events (which are events that are serious or life-threatening and unanticipated (or anticipated but occurring with a greater frequency than expected) and possibly, probably, or definitely related) or unanticipated problems involving risks to subjects or others will be reported in writing within 48 hours to

the IRB (using the appropriate forms from the website) and any appropriate funding and regulatory agencies. The investigator will apprise fellow investigators and study personnel of all adverse events that occur during the conduct of this research project through regular study meetings.

- d. For multi-site studies for which the Yale PI serves as the lead investigator:
- i. How will adverse events and unanticipated problems involving risks to subjects or others be reported, reviewed and managed?
 - ii. What provisions are in place for management of interim results?
 - iii. What will the multi-site process be for protocol modifications?

12. **Statistical Considerations:** Describe the statistical analyses that support the study design.
13.

Primary Outcome:

Incidence of delirium per admission of medical geriatric patients

Incidence of delirium per patient days of hospitalization in medical admission of geriatric patients

Secondary outcomes:

Risk factors associated with incident delirium

Duration of delirium by study group

Hospital length of stay

Sample size based was estimated using openepi.com (similar results with Stata version 14 sample size calculator) based on control group incidence of delirium in medical subgroup of 30%. (Chen et al: Exogenous melatonin for delirium prevention: a meta-analysis of randomized controlled trials - Molecular Neurobiology online publication 21 July 2015) with relative risk reduction of 30 %.

Sample Size: X-Sectional, Cohort, & Randomized Clinical Trials

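### The delirium exclusion has no look-back over the admission, so an episode that began before entry may be enrolled and later counted as incident delirium

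*Combined protocol and SAP*

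**What the plan says.** - **Criterion (Section V.7).** The only delirium exclusion is "Presence of delirium at the time of randomization". Where the protocol wants a look-back it writes one. The neighbouring criterion reads "Already taking melatonin at the time of randomization (at least one dose taken in the prior week", and ramelteon is handled in the same way.
- **How it is applied (Section V.8).** After the word-recall test, review of the consent form and teach-back, "A Short CAM will then be performed by the investigator to evaluate for delirium". The entry rule follows: "If delirium is not diagnosed via the Short CAM, the consent form will be completed and the patient entered into the trial".
- **Chart screen (Sections V.8, VII.3 and VII.6).** The team uses the EMR to "screen admissions to the four participating general Internal Medicine floors for eligibility, based on the above inclusion and exclusion criteria". Section VII.6 adds possible discussion with the primary team. Both steps apply the same list of criteria.
- **Earlier evidence (Section V.3).** The protocol notes that "it is considered standard of care for nurses to administer the Short CAM once daily at Yale-New Haven Hospital", and that one of the four floors, Verdi 4 West, does so twice daily. Consent may come up to 24 hours after arrival on the floor.
- **Nature of the condition (Section V.2).** Delirium is "characterized by fluctuating disturbances in consciousness".
- **Endpoint (Sections V.3 and V.12).** The endpoint is delirium on the Short CAM by discharge or before hospital day 15. The first primary outcome is "Incidence of delirium per admission of medical geriatric patients". Nothing separates a continuing or returning episode from a new one.

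**The concern.** The trial asks whether melatonin prevents delirium. If a patient has already been delirious in this admission, incidence per admission is settled for that patient before the first capsule. One negative assessment does not show that the admission has been free of delirium when the condition fluctuates by the protocol's own description.

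Take a patient who is positive at a morning nurse check, attentive at an afternoon consent visit, and positive again that evening. On the entry rule in Section V.8 this patient may be enrolled, and the evening result is then recorded as the primary endpoint. Events of this kind would occur in both arms. If melatonin does not change them, they pull the risk ratio towards 1 and reduce power. They would also enter the person-days analysis as early events.

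**Working it through.** **Plan's own figure.** Inputs from Section V.12: control risk 30%, melatonin risk 21% (risk ratio 0.70), two-sided alpha 0.05, power 80%, allocation 1:1. With the Fleiss formula without continuity correction,

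n per arm = [1.96 × √(2 × p̄ × (1 − p̄)) + 0.842 × √(p₁(1 − p₁) + p₂(1 − p₂))]² / (p₁ − p₂)², where p̄ = 0.255,

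the result is 366.99, or 367 per arm and 734 in total. This matches the plan. Power at 367 per arm is 80.0%, and Section V.12 shows no allowance above that number.

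**Dilution model.** The documents give no figure for f or r, so both are assumptions:
- f = share of subjects in each arm with delirium earlier in the admission
- r = probability that such a subject is CAM-positive after entry
- melatonin has no effect on r

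Observed risks:
- control = (1 − f) × 0.30 + f × r
- melatonin = (1 − f) × 0.21 + f × r

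Worked example, f = 5% and r = 100%: control = 0.95 × 0.30 + 0.05 = 0.335; melatonin = 0.95 × 0.21 + 0.05 = 0.2495; ratio = 0.2495 / 0.335 = 0.745.

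| f | r | Control | Melatonin | Risk ratio | Power at 367 per arm | n per arm for 80% | Share of control events from earlier delirium (f × r / control) |
|---|---|---|---|---|---|---|---|
| 0 | – | 30.0% | 21.0% | 0.700 | 80.0% | 367 | 0 |
| 2% | 30% | 30.0% | 21.2% | 0.706 | 78.3% | 384 | 2.0% |
| 2% | 70% | 30.8% | 22.0% | 0.714 | 77.5% | 391 | 4.5% |
| 2% | 100% | 31.4% | 22.6% | 0.719 | 76.9% | 397 | 6.4% |
| 5% | 30% | 30.0% | 21.5% | 0.715 | 75.6% | 410 | 5.0% |
| 5% | 70% | 32.0% | 23.5% | 0.733 | 73.6% | 430 | 10.9% |
| 5% | 100% | 33.5% | 25.0% | 0.745 | 72.2% | 443 | 14.9% |

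Of 734 subjects, 2% is about 15 and 5% about 37.

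**Do other provisions close the gap?**
- The chart screen works from the same criteria, so it carries no instruction to act on an earlier positive CAM.
- The three-word recall tests memory at that visit and is not a delirium history.
- The independent geriatrician (Section V.12) rules on whether delirium occurred when a CAM is equivocal, not on whether it began before entry.

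**The case against.** A reader might infer that every such patient passes screening and is enrolled. The documents do not support that. The chart is reviewed before approach, the treating team may be consulted, and recall and teach-back come before the CAM. The criterion speaks of the presence of delirium, and a screener could read a lucid interval as delirium still present. What stands against this is that the entry rule in Section V.8 turns on the one Short CAM, so the two readings can lead to different decisions by different recruiters.

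Further points in the plan's favour:
- **Little earlier evidence.** Three of the four floors do one routine CAM a day and consent falls within 24 hours of floor arrival, so there will often be no more than about one earlier nurse result. The documents describe no CAM before the floor. This limits both the problem and the yield of the fix.
- **Precedent.** The background table lists delirium at enrolment as an exclusion in the cited 378-patient hip-surgery trial. That makes the choice a recognised one; it does not supply a look-back.
- **Assumed sizes.** f has no source. Full recurrence is the extreme case. The same table reports a shorter duration of delirium on melatonin in that hip-surgery trial, so a later positive CAM might be affected by the drug. The table lists no baseline-delirium exclusion for the medical-service trial (31% on placebo), so the 30% planning rate may already contain such cases.

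It is also tempting to infer a bias in favour of melatonin, or an imbalance caused by the extra CAMs on Verdi 4 West. Neither follows. Allocation is randomised and blinded, and the floor difference is not a difference between arms.

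**Conclusion.** The point holds as a gap in the entry rule. The criteria permit, but do not require, enrolment of a patient with delirium earlier in the same admission, and any later positive CAM in that patient counts as an incident case. The consequence is non-differential dilution towards a risk ratio of 1, which cannot create a false benefit.

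On the assumed range (f 2% to 5%, r 30% to 100%, no drug effect in these subjects) the risk ratio moves from 0.70 to about 0.71 to 0.74 and power from 80% to between 78% and 72%. The true size could be smaller, and the documents cannot settle it. The sample size is correct on its own inputs. This is a cheap improvement of low to moderate severity.

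**What to change.** **Preferred.** Reword the exclusion in Section V.7 as: *delirium at randomisation, or a positive (non-equivocal) CAM or documented delirium earlier in the current hospital admission*. Check it in the EPIC review that already precedes approach, in addition to the investigator's Short CAM. The qualifier matters because Section V.12 recognises that some CAM results are equivocal, and one doubtful nurse result should not exclude a patient automatically.

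**Minimum, with no new exclusion.** Record any earlier positive CAM or charted delirium at baseline, and pre-specify in Section V.12 a sensitivity analysis of the primary outcome without those subjects.

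**Cost.** The preferred change takes one sentence and one checklist item, and a small number of patients become ineligible (about 15 to 37 per 734 if the assumed 2% to 5% is right). The minimum change costs one baseline field and one extra analysis.
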